8.1.2. Sino-Nasal Outcome Test (SNOT-22)

The SNOT-22 is a 22-item outcome measure on a 5-category scale applicable to sino-nasal conditions and surgical treatments. For each item, the score ranges from 0 (No problem at all) to 5 (Problem as bad as it can be), and hence for the 22-items, the total score ranges from 0 to 110. Higher total scores on the SNOT-22 imply greater impact of CRS on QoL.

The SNOT-22 will be completed as indicated in the SoA (see Section 3.9) and is located on the clinical tablet. This frequent SNOT-22 might provide a kinetic profile of etokimab efficacy in subjects with CRSwNP.

For analysis purposes, baseline SNOT-22 score will be defined as the last value reported on or prior to the first dose date (Day 1). Total SNOT-22 values will also be obtained at each visit during Treatment Period (Week 4, 8, 12 and 16), and at the end of the Safety Follow-up Period (Week 24). A listing of SNOT-22 score and the change from baseline will be provided per visit per subject.

8.1.2.1. Definition of Estimand

The SNOT-22 is measured every 4 weeks during treatment and at end of treatment (Week 16). The primary time point is Week 16. A general linear MMRM using the change from baseline in SNOT-22 scores at Weeks 4, 8, 12, and 16 as response; baseline (Day 1) SNOT-22 score as fixed covariate; treatment group, randomization stratification factor, time (Weeks 4, 8, 12, and 16), and treatment by time interaction as fixed effect; and subject as a random effect will be used to obtain least squares means to compare the etokimab treatment arms with the placebo arm.

Summary statistics for each time point will include n, mean, standard deviation, median, minimum, and maximum, for baseline, each time of measurement, and the change from baseline calculated as post baseline value minus the baseline value.

Subjects are also asked to choose the maximum of 5 most important items that are affecting their health at each SNOT-22 assessment. A summary table for each time point will be provided including the frequency and percentage of each item chosen as the top 5 items.

8.1.2.2. *Primary Statistical Analysis for SNOT-22*

The (co)primary hypothesis to be tested for this estimand is that treatment of adults diagnosed with CRSwNP using etokimab will result in a significantly greater reduction of Week 16 SNOT-22 from baseline when compared to placebo. This hypothesis will be tested by comparing the least squares adjusted means for each etokimab dose group with placebo, at the Week 16 time point. Comparison of each treatment arm with placebo will be based on the Week 16 least squares means obtained from the MMRM, where missing data due to dropouts are regarded as missing at random (MAR). The same procedure employed to NPS will be repeated for the primary statistical analysis of SNOT-22.

Graphical displays of the results will be presented. The (by time-point) least squares means and two-sided 95% confidence intervals for each treatment depicted with error bars will be plotted against time, and the p-values for the Week 16 comparisons will be displayed on the Week 16 time point.

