2 INTRODUCTION

2.1 STUDY RATIONALE

Chronic rhinosinusitis (CRS) is a heterogeneous disease which manifests with mucosal inflammation of the nasal cavity and paranasal sinuses. Chronic rhinosinusitis can be divided into 3 distinct clinical syndromes: CRS with nasal polyposis (CRSwNP) accounting for 20 to 33 percent of all CRS cases, and CRS without nasal polyposis and allergic fungal rhinosinusitis accounting for 60 to 65% and 8 to 12% of all CRS cases, respectively (*Meltzer et al., 2004*). CRSwNP is characterized by the presence of multiple polyps in the upper nasal cavity, originating from the ostiomeatal complex. It is the most aggressive form of CRS and causes significant morbidity and leads to a diminished quality of life in CRS patients.

Current treatment options for CRSwNP are limited and typically include nonsystemic treatment with nasal corticosteroids, systemic corticosteroids, antibiotic therapy, and the surgical removal of polyps. Many patients achieve disease control with these standard nonsystemic treatments. However, due to disease severity, treatment-related adverse reactions, or other factors, some patients do not achieve adequate disease control. Relapses after surgery are common in patients with CRSwNP, and thus, there is need for long term therapeutic control in CRS patients.

CRSwNP is often associated with other atopic diseases, with up to 50% of CRSwNP presenting with comorbid asthma (*Jarvis et al., 2012*) though the contributions of these acute conditions to the development of CRSwNP is not well understood. Asthma has been the most well-defined; approximately 88% of patients with asthma also have radiographic evidence of sino-nasal inflammation and approximately 26 to 48% of patients with asthma also have been diagnosed with CRSwNP. Increased asthma severity has been linked to enhanced sino-nasal inflammation (*Stevens, et al., 2016*).

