3.6. Determination of Sample Size

The two co-primary endpoints were assessed in order to determine the sample size that will provide adequate power to detect a clinically meaningful difference between each etokimab dosing regimen and placebo.

Sample size estimates were calculated based on the following assumptions:

- Overall alpha=0.05
- Co-primary endpoints
- Hierarchical testing of the 2 active treatment arms versus placebo

Based on data from similar trials conducted in adult subjects with CRSwNP, a difference in NPS of 1.3 between the etokimab change from baseline to week 16 and the placebo group change from baseline to week 16 will be clinically meaningful (*Bachert et al. 2016*). Assuming a standard deviation of 1.5, and a significance level of 5%, a sample size of n=27 for each treatment arm will provide approximately 87% power to detect the stipulated difference. In order to account for the dilution of treatment effect due to 18% dropouts and missing data, approximately 33 subjects are planned to be randomized equally to each of the three treatment arms.

The second co-primary endpoint is SNOT-22 total score. In a trial of adults with CRSwNP, the difference in mean change from baseline to Week 16 between active and placebo was 18.1. Assuming a common standard deviation of 19.2, and 2-sided significance level of 5%, the sample size of 27 subjects provides 92% power to detect the stipulated treatment difference. Hence, adjusting for 18% dropouts and missing data, n=33 subjects will provide >85% desired power to detect a clinically meaningful difference in this endpoint between each active arm and placebo.

Each co-primary endpoint will will be tested against two-sided alpha=0.05; therefore, the combined power for the testing of both endpoints is approximately 80%, assuming no negative correlation between endpoints.

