8.1. Primary Efficacy Endpoint and Analysis

Statistical hypotheses associated with the co-primary efficacy endpoints are as follows:

- Treatment of adults diagnosed with CRSwNP using etokimab will result in a significantly greater reduction of Week 16 NPS from baseline when compared to placebo, and
- Treatment of adults diagnosed with CRSwNP using etokimab will result in a significantly greater reduction of Week 16 SNOT-22 score from baseline when compared to placebo

Statistical significance for the co-primary efficacy endpoints will be declared if and only if both 2-sided pvalues for the tests of the individual hypotheses are < 0.05. Testing will be conducted in a hierarchical manner for each co-primary endpoint such that the comparison of the etokimab Q4W treatment arm versus placebo will be conducted first. If the result from this test is statistically significant, then the comparison of the etokimab Q8W treatment arm versus placebo will be performed. If the result from the etokimab Q4W versus placebo is not statistically significant, no further testing will be performed for the etokimab Q8W treatment arm versus placebo.

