8.1.1.2. Primary Statistical Analysis for NPS

Statistical analysis of this endpoint will employ a general linear model with repeated measures (also called a mixed model with repeated measures, MMRM), with the change from baseline in NPS as the dependent variable; baseline (Day 1) NPS score as a covariate, treatment group (3 levels), stratification factor, treatment by stratification factor, categorical time points (Weeks 4, 8, 12 and 16) and treatment by time interaction as fixed effect factors, and subject as a random effect in the model. Assuming treatment (trtpn) is coded as Placebo=1, Eto Q8W=2, Eto Q4W=3, and that the time variable (weekn) is ordered as 4, 8, 12, and 16, we can write the SAS model of interest to be performed with SAS PROCEDURE MIXED as follows:

```
PROC MIXED DATA = DATASETNAME;
CLASS USUBJID WEEKN TRTPN STRAT;
MODEL CFB = BASE STRAT TRTPN STRAT*TRTPN WEEKN WEEKN*TRTPN / SOLUTION DDFM=KR;
REPEATED WEEKN / SUBJECT=USUBJID TYPE=UN;
LSMEANS WEEKN*TRTPN / CL ALPHA=0.05;
RUN;
```

The (co)primary hypothesis to be tested for this estimand is that treatment of adults diagnosed with CRSwNP using etokimab will result in a significantly greater reduction of Week 16 NPS from baseline when compared to placebo.

This hypothesis will be tested by comparing the least squares adjusted means for each etokimab dose group with placebo, at the week 16 time point. Comparison of each treatment arm with placebo will be based on the change in least squares means at Week 16 obtained from the MMRM. Testing will be conducted in a hierarchical manner such that the comparison of the etokimab Q4W treatment arm versus placebo will be conducted first.

If the results of the comparison of the eetokimab Q4W treatment arm versus placebo are statistically significant, the etokimab Q8W treatment arm will be compared to placebo.

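### The SAP gives two different models for the SNOT-22 co-primary, and the one with treatment-by-asthma weights the asthma strata equally, which may cost power if the asthma share is far from 50%

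*SAP*

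**What the plan says.** For NPS, SAP 8.1.1.2 codes "MODEL CFB = BASE STRAT TRTPN STRAT*TRTPN WEEKN WEEKN*TRTPN" and requests "LSMEANS WEEKN*TRTPN / CL ALPHA=0.05". The model has a treatment-by-asthma term that is constant over visits. The LS means statement carries no observed-margins (OM) option.

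For SNOT-22 the SAP describes the model twice:

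- 8.1.2.1 gives the factors as "treatment group, randomization stratification factor, time (Weeks 4, 8, 12, and 16), and treatment by time interaction as fixed effect", plus baseline and subject, and says this model yields the LS means for comparing the arms.
- 8.1.2.2 says "The same procedure employed to NPS will be repeated for the primary statistical analysis of SNOT-22".

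Protocol Table 3 and 9.4.2.1.2 also apply the NPS model to SNOT-22, and the NPS model in Table 3 and 9.4.2.1.1 includes treatment by stratification factor. SAP Section 12 lists only the change to nocturnal awakenings.

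Success on the co-primaries is "declared if and only if both 2-sided" p-values are below 0.05 (SAP 8.1). SAP 3.6 sizes the trial as a plain two-group comparison on each endpoint and does not mention strata. The only figure for the share of CRSwNP patients with asthma is background, in protocol 2.1: "with up to 50% of CRSwNP presenting with comorbid asthma".

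**The concern.** There are two issues of different weight.

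First, a co-primary analysis should be specified once. Here two sections of the SAP, both in operative language, give models that differ by a term affecting the treatment contrast. Success requires SNOT-22 to be significant, and the Q8W comparison and all the secondary tests follow from that result. Two available p-values for a deciding test leave a choice that could later look data-driven, particularly since SAP 11.2 sends unblinded Week 8 co-primary results to designated sponsor personnel.

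Second, once treatment-by-stratum is in the model, the Week 16 treatment difference depends on how the strata are weighted. Without OM, each stratum gets one half. No section says that a half-asthma population is the intended target, and the sample size makes no allowance for the extra variance that equal weighting brings when the strata are unequal.

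**Working it through.** **Inputs.** From SAP 3.6: "Overall alpha=0.05"; "a difference in NPS of 1.3" with SD 1.5; SNOT-22 difference 18.1 with SD 19.2; 27 evaluable subjects per arm. From SAP 8.1: two-sided 0.05 on each endpoint. Assumed, because the documents do not give them: asthma share p (25% to 50%, equal in all arms) and within-subject correlation rho (compound symmetry, 0.3 to 0.7). Also assumed: complete data, no credit for baseline adjustment, and independent endpoints for joint power.

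**Step 1: reproduce the plan.** The standard error of a treatment difference is SD x sqrt(2/27).

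- NPS: 1.5 x 0.272 = 0.408; noncentrality 1.3/0.408 = 3.18; noncentral-t power on 52 df = 87.8% (stated: about 87%).
- SNOT-22: 19.2 x 0.272 = 5.23; noncentrality 18.1/5.23 = 3.46; power 92.5% (stated: 92%).
- Joint: 0.878 x 0.925 = 81.2% (stated: about 80%).

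**Step 2: variance factor from equal weighting.** The equally weighted Week 16 difference equals the share-weighted difference plus (0.5 - p) times the estimated interaction. These two parts are uncorrelated. The interaction is one time-constant effect, estimated from all four visits. Under compound symmetry, the mean of four visits has variance (1 + 3 rho)/4 times that of a single visit. So

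F = 1 + [(0.5 - p)^2 / (p(1 - p))] x (1 + 3 rho)/4.

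At p = 0.30 the bracket is 0.04/0.21 = 0.190. With rho = 0.3, F = 1 + 0.190 x 0.475 = 1.09. With rho = 0.7, F = 1 + 0.190 x 0.775 = 1.15. A direct generalised-least-squares calculation gives the same values. It also returns F = 1.00 in every case when the strata are weighted by their observed shares or the interaction is dropped.

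**Step 3: power.** Divide each noncentrality by sqrt(F). Ranges run over rho = 0.3 to 0.7, and both models are taken to carry the term.

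| Asthma share | F | NPS power | SNOT-22 power | Joint power |
|---|---|---|---|---|
| 50% | 1.00 | 88% | 92% | 81% |
| 40% | 1.02-1.03 | 87% | 92% | 80% |
| 30% | 1.09-1.15 | 83-85% | 89-90% | 74-77% |
| 25% | 1.16-1.26 | 80-83% | 86-88% | 68-73% |

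The table is symmetric about 50%: a 70% share gives the 30% row.

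**Step 4: how far apart the two SNOT-22 models can be.** Even with no true interaction, the two estimates differ by (0.5 - p) times the estimated interaction. The SD of that difference is sqrt(F - 1) standard errors.

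- At 40%: 0.14 to 0.18 of a standard error, or 0.7 to 0.9 SNOT-22 points (x 5.23).
- At 30%: 0.30 to 0.38, or 1.6 to 2.0 points.
- At exactly 50%: zero.

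A result near p = 0.05 could therefore fall on either side of the line, depending on which section is followed.

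**Step 5: possible offset.** A correlation r between baseline and change multiplies the variance by 1 - r^2. It cancels F when r = sqrt(1 - 1/F). This is about 0.29 to 0.36 at a 30% share and 0.37 to 0.45 at 25%. The documents give no value for r.

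**The case against.** The best defence is that the intended SNOT-22 model is not really in doubt. SAP 8.1.2.2 is the section headed as the primary analysis, the protocol agrees with it, the SAP's other full-population MMRMs carry treatment-by-stratum, and Section 12 records no departure. On that reading, 8.1.2.1 merely dropped a phrase. This is probably right and it bears on the remedy: 8.1.2.1 should not be adopted merely because it is simpler. It does not remove the contradiction, because 8.1.2.1 also says that its model produces the LS means for the comparison.

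On weighting, equal stratum weights are a legitimate prespecified choice. They do not inflate type I error, and they target the same effect if asthma does not modify it. That stands, so calling the 50:50 contrast an error would go too far. What remains is that the plan nowhere states the choice or allows for it.

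Two stronger readings are tempting. One is that the interaction term costs power outright. The documents do not support this: the cost is zero at a 50% share and about one point at 40%, no share is stated for this trial, and the 25-30% rows have no anchor in the text. The other is to use the single-visit factor 1/(4p(1 - p)), which gives 1.19 at 30% and 1.33 at 25%. That ignores the pooling of the interaction over four visits. Under compound symmetry it is reached only as rho approaches 1.

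**Conclusion.** The contradiction between SAP 8.1.2.1 and 8.1.2.2 is established from the text whatever the asthma share, and it should be corrected because it concerns a deciding p-value. Its practical effect grows as the share moves away from 50%.

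The power point is conditional. It is negligible between about 40% and 60% asthma. At 30%, NPS power sits at or just below the protocol's 85% target and joint power loses about 4 to 7 points from 81%. At 25%, the joint loss is about 8 to 13 points. Baseline adjustment, for which the plan takes no credit, could recover some or all of this. The equal weighting itself follows directly from the coded statement. The power figures rest on the assumptions listed with the calculation and should be read as a range, not a forecast.

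**What to change.** Before the interim unblinding, state one SNOT-22 model, identical in form to the NPS model, in SAP 8.1.2.1 and 8.1.2.2. There are two acceptable routes:

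1. **Smallest change.** Keep the protocol model, add treatment-by-stratum to 8.1.2.1, and add OM to the LSMEANS statement for both co-primaries so that strata are weighted by their observed shares, with the same weights in every arm. State those weights in the text.
2. **Alternative.** Drop STRAT*TRTPN from both primary models, leave treatment-by-asthma to the subgroup analysis already planned in SAP 6.6, and record the departure from protocol Table 3 in SAP Section 12.

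Either route restores the variance factor to 1.00. The cost is a few lines of SAP text and one change to the code. No data or subjects are affected.

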8.1.2.3. Supplementary Statistical Analysis for SNOT-22

In order to assess the impact of missing data due to dropouts, sensitivity analyses will be performed where their data after dropout will be imputed using multiple imputation and the statistical analysis using MMRM will be repeated. The same supplementary analysis listed in section 8.1.1.3 will be performed for SNOT-22.

8.2. Secondary Efficacy Endpoint(s) and Analyses

Analysis of secondary efficacy endpoints will be performed in a hierarchical order to adjust for statistical multiplicity.

If the co-primary efficacy endpoints show statistical significance at the 2-sided significance level of 0.05, the secondary efficacy endpoints will be first tested at the significance level of 0.05 in the following order for the etokimab Q4W treatment arm versus placebo, then they will be tested at the significance level of 0.05 in the same order for the etokimab Q8W treatment arm versus placebo. During the hierarchical testing of the secondary endpoints, if the analysis of a particular secondary endpoint results in a p-value ≥ 0.05 , the subsequent secondary endpoints will not be interpreted for statistical significance.

- 1. Time to first response (≥ 1 point improvement) in NPS
- 2. NPS response defined as a reduction of at least 1.0 from baseline to Week 16 in NPS
- 3. SNOT-22 response defined as a reduction of at least 12.0 from baseline to Week 16 in SNOT-22
- 4. Change from baseline to Week 16 in sense of smell as assessed by the University of Pennsylvania Smell Identification Test (UPSIT)

8.2.1. Time to First Response (\geq 1 Point Reduction in NPS)

Time to first response (≥ 1 point reduction in NPS), TTFR, is defined as the number of days from the first dose date to the date of a subject's first ≥ 1 point reduction in NPS, if a subject experiences a ≥ 1 point reduction in NPS. It will be calculated as:

TTFR = Date of first occurrence of ≥ 1 point reduction in NPS – date of first dose + 1

It is conceivable that a subject may achieve $a \ge 1$ point reduction and lose it on the next visit. This endpoint only analyzes the time to the first response. Subjects who do not have an on-study occurrence of $a \ge 1$ point reduction in NPS will have their TTFR censored at the last study evaluation time point in which NPS was collected. It will be calculated as:

TTFR = Last date of study evaluation of NPS - date of first dose + 1

The TTFR survivor functions will be estimated and plotted using the Kaplan-Meier method.

The logrank test stratified by the randomization factor will be performed for each etokimab dose regimen to evaluate whether it has a shorter time to first response than the Placebo group. The null hypothesis is that there is no treatment difference in the probability of achieving a ≥ 1 point reduction in NPS at any time during treatment; in other words, that the survivor functions for the time to ≥ 1 point reduction in NPS coincide. The alternative hypothesis is that the survivor functions are different.

A statistically significant shorter time to response (logrank test 2-sided p-value < 0.05) for the etokimab dose group when compared to the Placebo group will be taken as evidence in favor of efficacy of etokimab compared to placebo.

Summaries from the analysis will include a Kaplan-Meier plot of the survivor functions, a table summarizing the number of subjects in each treatment group, the number of events, the number censored, and the 25th and 75th percentile survival time estimate and median survival time estimate and their 95% CI, if estimable, and the p-value of the logrank test. A listing for each subject's time to first response will be provided.

The logrank test is based on the assumptions that the censoring mechanism is independent of the occurrence of an event (achieving ≥ 1 point reduction in NPS), the survival probabilities are the same for subjects recruited early and late in the study, and the events happened at the times specified. Events may not necessarily have occurred at the clinic visits, but they are ascertained at those visits. Since clinic visits are equally spaced and planned per protocol, we may regard this last assumption to be loosely satisfied. A more accurate assessment will require use of methods for handling interval censored data. In other words, since NPS is measured only at clinic visits, this endpoint may be interval censored: a subject's ≥ 1 point reduction could occur at time points between clinic visits but no NPS measurements are taken in between planned clinic visits. If deemed important and necessary, statistical methods appropriate for interval censored data may be explored and implemented.

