6.5.1 RESCUE MEDICINE

Use of rescue medication (eg, systemic corticosteroid) is not permitted in this study (except MFNS as supplied per protocol). If a subject receives systemic rescue treatment the subject will be discontinued from the study and should return for a final Early Termination Visit (ETV) within 30 days from last dose. Study procedures should be completed according to the ETV/EOS per Section 1.3. In the case of ongoing AEs/SAEs, the subject should be followed up until it has resolved or stable outcome or subject is lost to follow-up. The date and time of rescue medication administration, as well as the name and dosage regimen of the rescue medication, must be recorded into the eCRF/study database by study center personnel.

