8.2.2. Responder Analysis: Week 16 NPS Score Decrease of ≥1 from Baseline

One of the (co)primary endpoints is the change from baseline in NPS score at Week 16. For this variable, a responder may be defined as a subject whose NPS score at Week 16 decreased from baseline by at least 1.0. If

the subject did not make it to Week 16, or if the subject did not achieve an NPS score reduction ≥ 1 , the subject will be deemed a "Non-responder" (Response='No').

Summary statistics for each treatment group will include the number (n) and percentage (%) of subjects who responded, and an exact confidence interval for the % responders.

A logistic regression will be employed with terms for treatment (3 levels: 1=Placebo, 2=Eto Q8W, 3=Eto Q4W), baseline as a continuous covariate, and stratification factor (asthma comorbidity:1=Yes, 0=No).

Using the logistic regression model, for each comparison of the etokimab groups with the Placebo group, the estimated odds ratio for the etokimab versus placebo odds of response, a 95% Confidence Interval for the odds ratio, and the p-value for that comparison will be displayed in the summary table.

It is expected that treatment with etokimab should lead to a greater odds of response vs. not responding, when compared to the Placebo group. A statistically significantly greater odds ratio for the etokimab vs. placebo group comparison will be taken as evidence of efficacy in favor of etokimab.

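### SAP 8.2.1 censors subjects who leave the study as treatment failures in the time to first NPS response, so the Kaplan-Meier curve shows too much response and the log-rank test is biased in a direction set by which arm the failures leave

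*SAP*

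**What the plan says.** SAP 8.2.1 has one rule for every subject without a one-point NPS reduction: they "will have their TTFR censored at the last study evaluation time point in which NPS was collected". The reason follow-up ended plays no part. "The TTFR survivor functions will be estimated and plotted using the Kaplan-Meier method", with the median and the 25th and 75th percentile times tabulated. "The logrank test stratified by the randomization factor will be performed for each etokimab dose regimen" against placebo. The null hypothesis is worded as no treatment difference in the probability of reaching the reduction at any time during treatment, and is then equated with coinciding survivor functions.

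The same section lists what the test needs: "The logrank test is based on the assumptions that the censoring mechanism is independent of the occurrence of an event". It goes on to discuss only whether events can be dated to clinic visits, and mentions methods for interval-censored data. It does not assess independent censoring.

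Protocol 6.5.1 states: "If a subject receives systemic rescue treatment the subject will be discontinued from the study". SAP 8.3.10 repeats this. Protocol 7.2 adds that an investigator may withdraw a subject for disease progression. Discontinuation of treatment because of a need for oral corticosteroids or polyp surgery is an exploratory endpoint, so the plan expects such cases.

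SAP 8.2.2, the next endpoint on the same NPS data, scores a subject as a non-responder if "the subject did not make it to Week 16, or if the subject did not achieve an NPS score reduction" of at least 1.

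**The concern.** Systemic rescue marks a subject who is doing badly, and it ends follow-up by rule. Censoring that subject at the last NPS treats the subject as exchangeable with those still in the study, that is, as likely to respond later as they are. This is the opposite of what the exit tells us. It also separates the analysis from the SAP's null: the probability of a response on treatment counts a failure who leaves as someone who did not respond, while Kaplan-Meier redistributes that subject's weight to those who stay.

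The position in the hierarchy raises the stake. Once both co-primaries succeed, "the secondary efficacy endpoints will be first tested at the significance level of 0.05" for Q4W and then for Q8W. This endpoint comes first. If it gives p of 0.05 or more for Q4W, the other three Q4W secondary endpoints are not interpreted and, on the natural reading, neither is the Q8W sequence.

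A related gap concerns post-rescue data. The Schedule of Activities includes endoscopy at the early termination visit, and SAP 6.4 maps that visit to an analysis visit. Nothing stops an NPS taken after rescue from counting as a first response.

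**Working it through.** **Plan's own figures.** The documents state no power, response rate or rescue rate for this endpoint. The arm size used below does reproduce: 27/(1 − 0.18) = 32.9, so 33 per arm. The NPS power behind the 27 also reproduces: noncentrality (1.3/1.5) × √(27/2) = 3.18 on 52 df gives 87.8%, against a stated 87% or so.

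**Effect on the curve.** Inputs: 33 per arm (Protocol 9.2) and NPS at Weeks 4, 8, 12 and 16 (Protocol 1.3). The counts of responders and failures are assumptions. Failures are capped at 6 of 33 (18%), the plan's whole allowance for dropouts and missing data from any cause. With d responders and w failures censored after each visit:

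- Kaplan-Meier: S = ∏(1 − d/n), where the next n equals n − d − w.
- Proportion who respond (cumulative incidence when failures are the only exits): Σd/33.

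Example with 12 responders (3 per visit) and 2 failures after each of Weeks 4, 8 and 12: S = 30/33 × 25/28 × 20/23 × 15/18 = 0.588, so 1 − S = 41.2%, against 12/33 = 36.4%.

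| Responders by visit | Failures censored after Weeks 4/8/12 | 1 − KM | Proportion responding | Excess (points) |
|---|---|---|---|---|
| 3/3/3/3 | 1/0/0 | 37.3% | 36.4% | 0.9 |
| 3/3/3/3 | 1/1/1 | 38.5% | 36.4% | 2.2 |
| 3/3/3/3 | 2/2/2 | 41.2% | 36.4% | 4.8 |
| 3/3/3/3 | 3/3/0 | 42.3% | 36.4% | 5.9 |
| 8/5/4/3 | 1/1/1 | 64.1% | 60.6% | 3.5 |
| 8/5/4/3 | 2/2/2 | 68.9% | 60.6% | 8.3 |

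The excess is zero only if no failure is censored before a later response.

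**Effect on the percentile times.** In the last row, 1 − KM is 24.2%, 40.7% and 55.5% at Weeks 4, 8 and 12. The proportion responding is 24.2%, 39.4% and 51.5%. Both place the 25th percentile at Week 8 and the median at Week 12. With visits four weeks apart, a percentile time moves only when the percentile lies between the two curves at a visit. It may be pulled early, but need not be.

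**Effect on the test.** Simulation of 4,000 trials per row, 33 per arm, two-sided 5% log-rank, unstratified. Assumptions: first responses fall 40/25/20/15% at Weeks 4/8/12/16; failures are subjects who would not have responded, leaving with equal chance after Week 4, 8 or 12. Entries are the chance of a significant result favoring etokimab.

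| Response, active/placebo | Failure exits, active/placebo | As planned | Failures kept as non-responders to Week 16 |
|---|---|---|---|
| 60%/35% | 5%/18% | 44.9% | 52.6% |
| 60%/35% | 9%/9% | 54.2% | 51.5% |
| 60%/35% | 18%/18% | 57.9% | 52.8% |
| 60%/35% | 18%/5% | 65.5% | 52.8% |
| 35%/35% | 5%/18% | 1.4% | 2.4% |
| 35%/35% | 18%/18% | 2.2% | 2.2% |
| 35%/35% | 18%/5% | 3.7% | 2.6% |

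The simulation error near 2.5% is √(0.025 × 0.975/4000) = 0.25 points, so 1.4% and 3.7% are real departures. The differences within the last column among the 60%/35% rows are simulation noise.

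**The case against.** Several counter-arguments have force.

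- **No inflated response rate is printed.** A reader might infer that the plan will report 1 minus Kaplan-Meier as a response percentage. It will not. SAP 8.2.1 tabulates subjects, events, censored counts and percentile times, so the crude proportion can be read off. The reported response percentage comes from SAP 8.2.2, which already scores these subjects as non-responders. This stands: the distortion is in the plotted curve, possibly the percentile times, and the test.
- **The censored log-rank is a legitimate test.** It compares the rate of response among subjects still in the study. That is true, and the tail errors above are errors only against the SAP's stated null. But the SAP did state that null, in terms of the probability of responding during treatment.
- **Few exits may qualify.** Only systemic rescue forces an exit. Withdrawal for progression is discretionary, and SAP 8.1.1.1 lets subjects who merely stop study drug stay on and remain at risk. This stands, and limits the point to failure exits.
- **SAP 8.2.2 measures something else.** A subject who responds at Week 4 and then leaves is an event in 8.2.1 and a non-responder in 8.2.2. The different handling is therefore not in itself a contradiction. It shows only that the plan already accepts exit as non-response for NPS.
- **It is a Phase 2 secondary endpoint behind two co-primaries.** Also true, but it is the one that opens the secondary sequence.

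**Conclusion.** The concern holds for exits due to treatment failure. That "the censoring mechanism is independent of the occurrence of an event" is not credible for subjects removed because of rescue or progression, and the survivor functions then do not represent the stated null. That much follows from the text.

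The size does not. The documents give 18% for all dropouts and missing data and no share for failures, so treating all 18% as failures is an upper case and not an expectation. On the assumed counts, the curve is too high by about 1 point with 1 failure in 33, 2 to 4 with 3, and 5 to 8 with 6.

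A reader might also infer that the rule costs etokimab power. The documents do not support a fixed direction. Failures mainly on placebo work against etokimab (44.9% against 52.6%; favorable-tail error 1.4%). Failures mainly on etokimab work for it (65.5% against 52.8%; 3.7%). Equal failures with a higher response rate on etokimab also work for it (57.9% against 52.8%). The reason to change is the estimand the SAP states. The simulated test was unstratified, whereas the planned one is stratified by asthma.

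**What to change.** Amend SAP 8.2.1 before unblinding:

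1. Keep subjects who leave because of systemic rescue, nasal polyp surgery or disease progression before any response in the risk set of the stratified log-rank test as non-responders to Week 16 (Day 113). Show response as cumulative incidence with those exits as the competing event.
2. State that an NPS taken after systemic rescue or polyp surgery, including at the early termination visit, does not count as a first response.
3. Leave other withdrawals censored at the last NPS, and keep the present rule as a sensitivity analysis.

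This does not make 8.2.1 identical to 8.2.2, which also scores other withdrawals as non-responders, and it need not.

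The cost is SAP wording and one extra estimator. The protocol already has the rescue date (6.5.1) and reasons for discontinuation (7.2) recorded in the eCRF. The downside is that where failure exits are equal between arms or more frequent on etokimab, the test will have less apparent power than under the present rule (52.8% against 57.9% and 65.5% in the cases above).
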